#### 19.2. Participating Site Responsibilities

Responsibilities delegated to participating sites are defined in an agreement between the Sponsor and the individual site. The Principal Investigator is responsible for trial conduct at the participating site.

### 19.3. AstraZeneca Responsibilities

AZ is responsible on behalf of the Sponsor for the manufacture, packing, labelling and distributing of trial drug to participating sites in accordance with Good Manufacturing Practice and all applicable local legislation. Responsibilities are defined in an agreement between AZ and the Sponsor.

#### 20.TRIAL ADMINISTRATION & LOGISTICS

# **20.1.** PHOENIX Participating Sites

PHOENIX will be opened across a network of approximately 20 Screening only and Treatment sites. It is the expectation that Screening Only Sites will identify and register patients with radiographically measurable tumour mass on standard of care imaging performed at the mid-assessment timepoint of SOC neoadjuvant treatment. Registered patients will then undergo protocol mandated end of neoadjuvant chemotherapy imaging, with patients eligible for Trial Entry (including residual disease ≥1cm) referred to an appropriate

IRAS Project Number: 249774

Treatment site for Trial Entry. After completion of trial follow-up the patient can be transferred back to the Screening Only Site for continued follow up according to standard and local practice.

#### 20.1.1. Screening Only Sites

Screening Only Site selection will be based on proximity to and natural referral into an open Treatment Site. The pairing of Screening Only and Treatment Sites will be determined at the time of site activation of the Screening Only Site.

Screening Only Centres will perform the following tasks:

- Approach patients and obtain consent for Trial Registration
- Transfer of patient's archival diagnostic tissue to the central laboratory for analysis
- Arrange and complete protocol-mandated imaging at the end of standard of care neoadjuvant chemotherapy
- Initiate the consent process for Trial Entry by providing the PHOENIX Trial Entry patient information sheet to potentially eligible patients in order to confirm that the patient is willing to be referred for consent at the Treatment Site
- Referral of patients to the Treatment Site for consent to Trial Entry as per local practice
- If applicable and appropriate, follow up once patient care is transferred back from the Treatment Site, upon completion of trial follow-up or on withdrawal from the trial.

**Please note:** Screening Only Sites should not consent patients for Trial Entry. This task should **only** be performed by the Treatment Site who will be responsible for consenting the patient to Trial Entry, cohort allocation and administration of trial treatment.

#### 20.1.2. Treatment Sites

Treatment Site selection will be based on experience in the delivery of early phase breast cancer trials and the ability to receive referrals from the Screening Only Sites.

Treatment Sites will perform the following tasks:

- Approach patients and obtain consent for Trial Registration
- Transfer of patient's archival diagnostic tissue to the central laboratory for analysis
- Arrange and complete protocol-mandated imaging at the end of standard of care neoadjuvant chemotherapy
- Obtain consent from potentially eligible patients for Trial Entry, including those patients referred from a Screening Only site
- Trial treatment administration in Part 1 (pre-surgical WOP) and Part 2 (post-surgery)
- Follow up of all patients for up to 24 months from the Part 2 pre-treatment assessment/ 3-month postsurgery visit, after which point standard of care follow up can be continued either at the Treatment Site or at the original referring Screening Only site.

#### 20.2. Site Activation

Before recruitment can commence at a site, the site agreement must have been signed by all required signatories, the required trial documentation (as specified by ICR-CTSU) must be in place and a site initiation must have taken place. Site initiation may be by teleconference or by on site visit if requested by the Principal

IRAS Project Number: 249774

Investigator or if deemed appropriate by ICR-CTSU. ICR-CTSU will provide the final confirmation that recruitment can commence at a site. This confirmation should be filed in the Site Investigator File. No patients should be registered until the site has received activation confirmation from ICR-CTSU.

### 20.3. Investigator Training

Training in the scoring of residual cancer burden (RCB) will be provided by a named site lead pathologist. Additionally, given as in exceptional cases, research biopsy cores may be taken by the surgeon intraoperatively (e.g. where radiologically guided biopsy of the post-window residual disease is not feasible), training will need to be provided by the site lead radiologist or surgeon.

#### 20.4. Data Acquisition

Electronic (e) Case Report Forms (CRFs) will be used for the collection of trial data and data should be entered into the clinical trial database in a timely manner. ICR-CTSU will provide guidance to sites to aid the completion of the eCRFs. The Trial Management Group reserves the right to amend or add to the eCRF template as appropriate. Such changes do not constitute a protocol amendment, and revised or additional forms should be used by sites in accordance with the guidelines provided by ICR-CTSU.

# 20.5. Central Data Monitoring

Once data has been entered on the eCRF by the site personnel, ICR-CTSU will review it for compliance with the protocol, and for inconsistent or missing data. Should any missing data or data anomalies be identified, queries will be raised for resolution by the site.

Any systematic inconsistencies identified through central data monitoring may trigger an on-site monitoring visit.

ICR-CTSU will also request from sites redacted copies of each patient's trial-specific imaging report and surgical pathology report for central monitoring purposes.

#### 20.6. On-Site Monitoring

If a monitoring visit is required, ICR-CTSU will contact the site to arrange the visit. Once a date has been confirmed, the site should ensure that full patient notes of participants selected for source data verification are available for monitoring.

ICR-CTSU staff conducting on-site monitoring will review essential documentation and carry out source data verification to confirm compliance with the protocol. If any problems are detected during the course of the monitoring visit, ICR-CTSU will work with the Principal Investigator or delegated individual to resolve issues and determine appropriate action.

#### 20.7. Completion of the Trial and Definition of Trial End Date

The trial end date is deemed to be the date of last data capture expected to be once all patients have completed 24 months of follow up in Part 2.

IRAS Project Number: 249774

### 20.8. Archiving

Essential trial documents should be retained according to local policy and for a sufficient period for possible inspection by the regulatory authorities (at least 5 years after the date of last data capture). Documents should be securely stored and access restricted to authorised personnel.

# 21.PATIENT PROTECTION AND ETHICAL CONSIDERATIONS

# 21.1. Sponsor Risk Assessment and Approvals

This trial has been formally assessed for risk and approved by the sponsor's Committee for Clinical Research (CCR).

ICR-CTSU, on behalf of the sponsor, will ensure that the trial has received ethics approval from a research ethics committee (REC) for multi-centre trials, regulatory approval from the MHRA and relevant NHS Permissions. Before recruiting patients, the Principal Investigator at each site is responsible for obtaining local approvals.

#### 21.2. Public and Patient Involvement

Patient advocate members were involved in protocol design including methodology, sample collection, patient information and consent forms and are represented on the TMG.

# 21.3. Ethics and Regulatory Approvals

The trial will not commence at any participating site until the required approvals are in place. The ICR-CTSU, on behalf of the Sponsor, will ensure that the trial has received ethics approval from a research ethics committee (REC) for multi-centre trials, regulatory approval from the MHRA and relevant NHS Permissions. Before recruiting patients, the Principal Investigator at each site is responsible for obtaining local approvals.

# 21.4. Trial Conduct

This trial will be conducted according to the approved protocol and its amendments, supplementary guidance and manuals supplied by the ICR-CTSU and in accordance with The Medicines for Human Use (Clinical Trials) Regulations 2004 as amended, the Research Governance Framework for Health and Social Care and the principles of GCP and relevant data protection legislation.

#### 21.5. Informed Consent

Patients should be asked to provide consent for a trial in a three-step process. Patients should be asked to sign the current ethics approved **PHOENIX ICF for Trial Registration** prior to Trial Registration. Patients who subsequently meet the eligibility criteria for Trial Entry should be asked to sign the current ethics approved **PHOENIX ICF for Trial Entry** prior to Trial Entry. Patients who are suitable for trial treatment in PART 2 should be asked to sign the current ethics approved **PHOENIX ICF forPART 2 Trial Treatment** prior to further trial treatment post-surgery.

IRAS Project Number: 249774

Consent should only be taken after receiving both verbal and written information about the trial, having been given sufficient time to consider this information. All consent forms must be countersigned by the Principal Investigator or a delegated individual. A signature log of delegated responsibilities, listing the designated individuals and the circumstances under which they may countersign consent forms, must be maintained at the participating site. This log, together with original copies of all signed patient consent forms, should be retained in the Site Investigator File and must be available for inspection. The current ethics approved PHOENIX patient information sheets should be provided in addition to any standard patient information sheets that are provided by the site and used in routine practice. The consent process including the version of PIS and consent form used should be documented in the patient's notes.

# 21.6. Discontinuation from Follow-up

If a patient withdraws from further follow-up a patient withdrawal form should be completed in the MACRO database stating whether the patient simply no longer wishes to attend trial follow up visits or whether the patient has withdrawn consent for any further information to be sent to the ICR-CTSU.

# 21.7. Patient Confidentiality

Patients will be asked to consent to their full name being collected at Trial Entry in addition to their date of birth, hospital number, postcode and NHS number or equivalent to allow linkage with routinely collected NHS data and ensure accuracy in handling biological samples.

Each investigator should keep a separate log of all participants' Registration Numbers, Trial IDs, names, addresses and hospital numbers. The investigator must retain trial documents (e.g. participants' written consent forms) in strict confidence. The investigator must ensure the participants' confidentiality is maintained at all times.

Representatives of ICR-CTSU and the regulatory authorities will require access to participants' hospital notes for quality assurance purposes. ICR-CTSU will maintain the confidentiality of participants at all times and will not reproduce or disclose any information by which participants could be identified.

### 21.8. Data Protection

All parties must comply with all applicable data protection laws.

#### 21.9. Insurance and Liability

The sponsor holds clinical trials insurance. Indemnity to meet the potential legal liability of investigators participating in this trial is provided by the usual NHS indemnity arrangements.

#### **22.FINANCIAL MATTERS**

This trial is investigator designed and led, has been endorsed by Clinical Research Committee (CRC) of Cancer Research UK, and meets the criteria for R&D support as outlined in the Statement of Partnership on Non-Commercial R&D in the NHS in England.

IRAS Project Number: 249774

The trial is part of the National Institute for Health Research Clinical Research Network (NIHR CRN) portfolio by virtue of its endorsement by CRC. NIHR CRN resources should therefore be made available for the trial to cover UK specific research costs.

The sponsor has received an Investigator Initiated Research (IIR) grant from AZ for the conduct of this trial.

# 23. PUBLICATION POLICY

The main trial results for each cohort will be published either separately or together in a peer-reviewed journal, on behalf of all collaborators. The manuscript will be prepared by a writing group, consisting of members of the TMG. Participating clinicians may be selected to join the writing group on the basis of intellectual and time input. All participating clinicians will be acknowledged in the publication.

Any presentations and publications relating to the trial must be authorised by the TMG. Authorship of any secondary publications e.g. those relating to sub-studies, will reflect intellectual and time input into these studies.

No investigator may present or attempt to publish data relating to the PHOENIX trial without prior permission from the TMG.

PHOENIX Protocol IRAS Project Number: 249774

# Section 24 PART 1: OLAPARIB MONOTHERAPY TRIAL TREATMENT INFORMATION COHORTS E-G

#### 24. PART 1 OLAPARIB MONOTHERAPY: TRIAL TREATMENT INFORMATION COHORTS E-G

#### 24.1. Part 1 Trial Treatment

Olaparib is the IMP for Cohorts E-G in Part 1.

# 24.1.1. Part 1 Olaparib: Dose and Schedule

Olaparib 300mg (2 x 150mg tablets) twice daily should be administered orally on Days 1–14 of the WOP.

Olaparib should be taken at the same time each day, approximately 12 hours apart with one glass of water. Olaparib tablets can be taken with or without food.

Trial treatment should be swallowed whole and not chewed, crushed, dissolved or divided.

It is prohibited to consume grapefruit juice while taking olaparib. In addition it is recommended that patients avoid the consumption of grapefruit hybrids, pummelos, star-fruit, Seville oranges or products containing the juice of any of these (such as marmalade) during treatment and preferably 7 days before the first dose of trial treatment.

# 24.1.2. Part 1 Olaparib: Duration of Trial Treatment

Patients will receive trial treatment for 14 days during the WOP from Day 1 to Day 14.

A patient is considered evaluable if they receive ≥80% of expected doses **and** receive both doses of olaparib on WOP D14.

### 24.1.3. Part 1 Olaparib: Dose Modifications

No dose modifications will apply in the WOP.

#### 24.1.4. Part 1 Olaparib: Discontinuation of Trial Treatment

Trial treatment should continue as instructed in the WOP unless the patient experiences unacceptable toxicity or withdraws consent.

#### 24.2. Part 1 Olaparib: Prescription and Dispensing

Olaparib tablets will be provided in non-patient-specific bottles. The patient's Trial ID should be recorded on the bottle label prior to dispensing. Patients should be instructed to keep their trial treatment in the bottles provided and not transfer it to any other container.

All efforts should be made to ensure that patients clearly understand the directions for self-medication. Patients should be given a sufficient supply and unused trial treatment and/or empty bottles should be returned at the appropriate time points. Returned unused trial treatment must not be redispensed to any patient and should only be destroyed with prior approval from ICR-CTSU according to local destruction policy.

Olaparib should be prescribed by the PI or Co-investigator and dispensed by the hospital pharmacy from trial stock supplied specifically for use within PHOENIX only.

# 24.3. Part 1 Olaparib: Patient Cards and Treatment Diary Cards

A small wallet sized patient card template will be provided by ICR-CTSU for completion by the participating site. Each card will state:

- The name of the participating site
- That the patient is participating in the PHOENIX trial
- That the patient is taking olaparib
- An emergency site contact number

Patients should be advised to keep their patient card in their possession at all times.

A treatment diary card will be provided by ICR-CTSU for completion by the patient, in order to record the number of tablets taken on each day of the WOP.

### 24.4. Part 1 Olaparib: Permitted Concomitant Therapy

Patients who are receiving neoadjuvant pembrolizumab as SOC can continue this treatment during Part 1 of the trial. All other medication considered necessary for the participants' welfare and which is not expected to interfere with the evaluation of the trial treatment may be given at the discretion of the investigator. All concomitant medications must be recorded in the patient's notes, as well as the appropriate eCRF pages within the clinical database.

The use of any natural/herbal products or other traditional remedies should be discouraged, but use of these products, as well as use of all vitamins, nutritional supplements, and all other concomitant medications must be recorded in the eCRF.

Bisphosphonates, RANK ligand antagonists (e.g. denosumab) and blood transfusions should be given as required at the discretion of the Investigator.

Patients may take corticosteroids but increased vigilance is recommended on electrolyte and glucose levels.

Patients who require anti-coagulation during trial treatment should start on LMWH.

#### 24.5. Part 1 Olaparib: Non-permissible Medications/Therapies

With the exception of pembrolizumab (as indicated in the section above) no other anti-cancer therapy (chemotherapy, immunotherapy other than pembrolizumab, hormonal therapy (Hormone replacement therapy is acceptable), radiotherapy, biological therapy or other novel agent) is to be permitted while the patient is receiving trial treatment during the 14-day pre-surgical WOP.

Live virus and live bacterial vaccines should not be administered whilst the patient is receiving trial treatment and during a period of 30 days following the last dose of trial treatment. An increased risk of infection by the

IRAS Project Number: 249774

administration of live virus and bacterial vaccines has been observed with conventional chemotherapy drugs and the effects with olaparib are unknown.

#### PLEASE REFER TO APPENDIX 6 FOR PROHIBITED CONCURRENT MEDICATIONS FOR OLAPARIB.

It is recommended that known potent inhibitors/inducers of CYP3A are not co-administered with olaparib. Please see Appendix 6 for details. The required washout period prior to commencing trial treatment is 5 weeks for known strong or moderate CYP3A inhibitors or inducers. Please refer to Section 8.1.2 Trial Entry Exclusion Criteria for further information.

Caution should be exercised when substrates of CYP3A4 or UGT1A1 are combined with olaparib, in particular those with a narrow therapeutic margin. Caution should be exercise if olaparib is administered in combination with P-gp inhibitors which may increase exposure to olaparib. Caution should be exercised if olaparib is administered in combination with any statin. **Please see Appendix 6 for additional guidance.** 

Based on limited *in vitro* data, olaparib may increase the exposure to substrates of CYP3A4, P-gp, OATP1B1, OCT1, OCT2, OAT3, MATE1 and MATE2K. Based on limited *in vitro* data, olaparib may reduce the exposure to substrates of CYP3A4, CYP1A2, 2B6, 2C9, 2C19 and P-gp. **Please see Appendix 6 for examples of substrates.** 

The efficacy of hormonal contraceptives may be reduced if co-administered with olaparib.

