#### PLEASE REFER TO APPENDIX 5 FOR PROHIBITED CONCURRENT MEDICATIONS FOR OLAPARIB.

It is recommended that known potent inhibitors/inducers of CYP3A are not co-administered with olaparib. Please see Appendix 5 for details. The required washout period prior to commencing trial treatment is 5 weeks for known strong or moderate CYP3A inhibitors or inducers. Please refer to Section 8.1.2 Trial Entry Exclusion Criteria for further information.

Caution should be exercised when substrates of CYP3A4 or UGT1A1 are combined with olaparib, in particular those with a narrow therapeutic margin. Caution should be exercise if olaparib is administered in

IRAS Project Number: 249774

combination with P-gp inhibitors which may increase exposure to olaparib. Caution should be exercised if olaparib is administered in combination with any statin. **Please see Appendix 5 for additional guidance.** 

Based on limited *in vitro* data, olaparib may increase the exposure to substrates of CYP3A4, P-gp, OATP1B1, OCT1, OCT2, OAT3, MATE1 and MATE2K. Based on limited *in vitro* data, olaparib may reduce the exposure to substrates of CYP3A4, CYP1A2, 2B6, 2C9, 2C19 and P-gp. **Please see Appendix 5 for examples of substrates.** 

The efficacy of hormonal contraceptives may be reduced if co-administered with olaparib.

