#### APPENDIX 5: OLAPARIB CONCOMITANT TREATMENT CAUTIONS AND RESTRICTIONS

## STRONG OR MODERATE CYP3A INHIBITORS

Known strong CYP3A inhibitors (e.g., itraconazole, telithromycin, clarithromycin, boosted protease inhibitors, indinavir, saquinavir, nelfinavir, boceprevir, telaprevir) or moderate CYP3A inhibitors (ciprofloxacin, erythromycin, diltiazem, fluconazole, verapamil) should not be taken with olaparib. If there is no suitable alternative concomitant medication then the dose of olaparib should be reduced for the period of concomitant administration.

Strong CYP3A inhibitors – reduce the dose of olaparib to 100mg BD for the duration of concomitant therapy with the strong inhibitor and for 5 half-lives afterwards.

Moderate CYP3A inhibitors – reduce the dose of olaparib to 150mg BD for the duration of concomitant therapy with the moderate inhibitor and for 3 half-lives afterwards.

After the washout of the inhibitor is complete, the olaparib dose can be re-escalated.

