#### STRONG OR MODERATE CYP3A INDUCERS

Strong (e.g., phenobarbital, phenytoin, rifampicin, rifabutin, rifapentine, carbamazepine, nevirapine, enzalutamide and St John's Wort) and moderate CYP3A inducers (e.g. bosentan, efavirenz, modafinil) of CYP3A should not be taken with olaparib. If the use of any strong or moderate CYP3A inducers are considered necessary for the patient's safety and welfare this could diminish the clinical efficacy of olaparib. If a patient requires use of a strong or moderate CYP3A inducer or inhibitor then they must be monitored carefully for any change in efficacy of olaparib.

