The possibility that olaparib may be an inhibitor of the hepatic uptake transporters OATP1B1, OATP1B3, OCT1 or NTCP was investigated. Olaparib was an inhibitor of OATP1B1 and the IC50 (20.3  $\mu$ M and 27.1  $\mu$ M) was dependent on the substrate used. Olaparib was an inhibitor of OCT1 (IC50 37.9  $\mu$ M), it caused no significant inhibition of OATP1B3 and was a very weak inhibitor of NTCP (IC50 >100  $\mu$ M). Regulatory criteria indicate olaparib has the potential to cause clinically significant inhibition of hepatic OATP1B1 and OCT1.

The capacity for olaparib to inhibit MDR1 (Pgp), BCRP and MRP-2 was investigated. MDR1 and BCRP were expressed in MDCKII cells while MRP-2 was prepared in isolated membrane vesicles. **Olaparib** was shown to inhibit MDR1 (IC50 76.0  $\mu$ M) and very weakly inhibit BCRP. Olaparib did not inhibit MRP-2. Regulatory criteria indicate olaparib has the potential to cause clinically significant inhibition of biliary and GI tract MDR1.

These findings suggest that olaparib has the potential to cause clinically significant interactions with other CYP3A4 substrates or UGT1A1 substrates in the liver or gastrointestinal (GI) tract. Therefore, caution should be exercised when substrates of CYP3A4 are combined with olaparib, in particular those with a narrow therapeutic margin (eg, simvastatin, cisapride, cyclosporine, ergot alkaloids, fentanyl, pimozide, sirolimus, tacrolimus and quetiapine). Substrates of UGT1A1 should also be given with caution in combination with olaparib (eg, irinotecan, nintedanib, ezetimibe, raltegravir and buprenorphine).

The likelihood that olaparib would inhibit the renal uptake and efflux transporters OCT2, OAT1, OAT3, MATE1 and MATE2K was investigated. Olaparib was able to inhibit OCT2 (IC50 19.9  $\mu$ M), OAT3 (IC50 18.4  $\mu$ M), MATE1 (IC50 5.50  $\mu$ M) and MATE2K (IC50 47.1  $\mu$ M). Olaparib had no significant effect on OAT1. Regulatory criteria indicate olaparib has the potential to cause clinically significant inhibition of renal OCT2, OAT3, MATE1 and MATE2K.

Table 2: Commonly used drugs used during anaesthesia (pre-operative, during surgery and post-operative)

Drug	Indication	Metabolic Summary	AZ opinion	Interaction
			on likelihood	Summary
			of	
			clinically	
			important	
			interaction	
			with	
			Olaparib	
Cyclizine	Anti-emetic	Limited information is available	Low	
		on metabolism and excretion.		
		Drug not recommended for		
		patients with liver failure. Drug		

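### Section 24.5 sends Part 1 sites to the anaesthetics appendix for olaparib's prohibited medicines; the restrictions and the interaction dose rule are in Appendix 5, and Section 24.1.3 conflicts on its face with that rule

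*Protocol*

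**What the plan says.** Section 24.5 (Part 1, Non-permissible Medications/Therapies) opens its interaction text with "PLEASE REFER TO APPENDIX 6 FOR PROHIBITED CONCURRENT MEDICATIONS FOR OLAPARIB". It names the same appendix three more times: for CYP3A inhibitor and inducer details, for additional guidance, and for examples of substrates.

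Section 25.2.8 carries nearly the same text for Part 2. There the instruction is "PLEASE REFER TO APPENDIX 5 FOR PROHIBITED CONCURRENT MEDICATIONS FOR OLAPARIB", and the three later references are also to Appendix 5.

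Appendix 5 covers cautions and restrictions on medicines taken with olaparib. It says that strong and moderate CYP3A inhibitors should be avoided, and then: "If there is no suitable alternative concomitant medication then the dose of olaparib should be reduced for the period of concomitant administration". For a strong inhibitor the instruction is to "reduce the dose of olaparib to 100mg BD for the duration of concomitant therapy with the strong inhibitor"; for a moderate one the dose is 150 mg BD. For a patient who needs a strong or moderate inducer or inhibitor it adds: "then they must be monitored carefully for any change in efficacy of olaparib".

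Appendix 6 covers possible interactions with anaesthetics. It consists of an investigator's brochure extract and a table of drugs used before, during and after surgery.

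On dosing in the window, Section 24.1.3 says in full: "No dose modifications will apply in the WOP". Section 24.1.4 says: "Trial treatment should continue as instructed in the WOP unless the patient experiences unacceptable toxicity or withdraws consent".

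**The concern.** There are two linked faults. First, a Part 1 site that follows Section 24.5 reaches an appendix written for another purpose. There it finds no list of prohibited medicines and no instruction on what to do with the olaparib dose. Second, if the reference is corrected, the site reaches a rule requiring a dose reduction, while Section 24.1.3 says that doses are not modified in the window.

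The situation at stake is narrow: a patient already taking olaparib in the window who newly needs a strong or moderate CYP3A inhibitor with no suitable alternative. The investigator could continue at 300 mg BD, reduce the dose or stop, and the protocol does not give one consistent answer. All patients in Cohorts E to G take olaparib in Part 1 under Section 24, so the text applies to every current participant even though the event should be rare.

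**Working it through.** No design figure is involved, so the check is a comparison of texts.

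**1. Which appendix is meant?**

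| Subject of the reference | Section 24.5 (Part 1) | Section 25.2.8 (Part 2) | Where the content is |
|---|---|---|---|
| Prohibited medicines | Appendix 6 | Appendix 5 | Appendix 5 |
| CYP3A inhibitor and inducer details | Appendix 6 | Appendix 5 | Appendix 5 |
| Additional guidance (substrates, P-gp inhibitors, statins) | Appendix 6 | Appendix 5 | Mainly Appendix 5, partly Appendix 6 |
| Substrate examples | Appendix 6 | Appendix 5 | Fuller list in Appendix 5, some in Appendix 6 |

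The first two references plainly miss. The last two miss only in part, because the brochure extract in Appendix 6 gives CYP3A4 substrate examples and says "Substrates of UGT1A1 should also be given with caution in combination with olaparib", with UGT1A1 examples that Appendix 5 lacks. Elsewhere Part 1 uses Appendix 6 for its proper purpose, the Day 14 anaesthetic review (Section 11.2 and footnote 7 to Section 11.5). So the protocol itself shows which reference is right.

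**2. Does the wrong reference change the instruction received?** For at least one drug it does. Appendix 5 lists erythromycin as a moderate CYP3A inhibitor to be avoided, with a reduction to 150 mg BD if it cannot be. The erythromycin row in Appendix 6 advises only caution when the two are combined and gives no olaparib dose.

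**3. Size of the reduction in question.** The planned dose is 300 mg BD.
- Strong inhibitor: 100/300 = 33% of each planned dose.
- Moderate inhibitor: 150/300 = 50% of each planned dose.

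**4. Which rule governs in the window?**
- Section 24.1.3 excludes dose modifications in the window, without qualification.
- Section 24.1.4 gives unacceptable toxicity and withdrawal of consent as the only grounds for departing from the planned treatment. An unavoidable interacting medicine is neither.
- Appendix 5 requires a reduction and is not limited to Part 2.
- None of the three refers to the others.

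Read literally, Sections 24.1.3 and 24.1.4 leave no room to reduce or to stop, while Appendix 5 requires a reduction. Section 25.2.2, the Part 2 section with the same title, is about toxicity, so Section 24.1.3 may be meant for toxicity only, but it does not say so.

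**The case against.** The strongest reply is that little practical harm can follow. Section 24.5 itself advises against potent CYP3A inhibitors and inducers, states a 5-week washout for strong or moderate ones, and refers to Section 8.1.2, which names the main drugs. Appendix 5 comes immediately before Appendix 6. Section 24.4 also limits discretionary medication to what is not expected to interfere with evaluating the trial treatment. All of this stands. A reader might infer that Part 1 sites cannot find out which medicines to avoid; the documents do not support that.

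A second reply is that there is no real conflict, since a specific rule for the window should override general olaparib guidance. That is a reasonable reading of Section 24.1.3, but it is not written down. Nor does it tell the investigator what to do when the inhibitor is medically necessary: on that reading the patient would stay on the full dose, which is what Appendix 5 is there to prevent. Section 8.1.2 does not help here, because it sets entry exclusions and washouts and not conduct during treatment.

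A third reply concerns exposure. A reader might infer that some patients could spend the whole window on one third or one half of the dose, and that the response rate would be diluted. The documents do not support this either. A patient on an inhibitor at the first dose is excluded by Section 8.1.2, and no frequency is given for a new need arising within 14 days.

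**Conclusion.** The wrong reference in Section 24.5 is certain: the content of both appendices and the parallel text in Section 25.2.8 show it. The conflict between Section 24.1.3 and Appendix 5 is real on the face of the text. It is less certain what Section 24.1.3 was meant to cover; an unstated limit to toxicity, or an unstated precedence over Appendix 5, would each resolve it.

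This is a small correction to a safety instruction. It matters only for a strong or moderate CYP3A inhibitor newly needed in the window with no alternative, which should be rare after the required washout. No effect on the Simon two-stage design in Cohort G or on the primary analysis is claimed. The evaluability rule in Section 24.1.2 counts doses taken and is silent on a reduced dose. That is a loose end only if reductions are allowed, and is not a separate fault.

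**What to change.** 1. In Section 24.5, change Appendix 6 to Appendix 5 at the four places. A secondary reference to Appendix 6 may stay for the UGT1A1 substrate examples. Leave Appendix 6 as it is for the Day 14 anaesthetic review.
2. In Section 24.1.3, say which rule governs. One option is to limit the sentence to toxicity and send an unavoidable strong or moderate CYP3A inhibitor to Appendix 5. The other is to require olaparib to stop, adding that reason to Section 24.1.4. A patient stopped before completing Day 14 would already be non-evaluable under Section 24.1.2.

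Optional: if reductions are allowed, say in Section 24.1.2 whether such a patient is evaluable; and add a reference to Appendix 5 in the erythromycin row of Appendix 6.

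The cost is four appendix numbers, about one sentence of protocol text and one medical decision (reduce or stop). The optional evaluability sentence would need a second decision. The sample size and the analysis do not change.
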